7.12.1.3 Data Collection and Follow Up for Withdrawn Participants

If a participant is discontinued prematurely from treatment or from the study, the reason for discontinuation will be collected in the eCRF.

For participants who discontinue from the study for reasons other than withdrawal of consent, lost to Follow up, or death, a reasonable effort should be made to complete certain study procedures at or near the time of discontinuation.

Any AEs that are present at the time of discontinuation/withdrawal should be followed in accordance with the safety requirements.

If a participant is lost to Follow-up, every reasonable effort must be made by the study site personnel to contact the participant and determine the reason for discontinuation/withdrawal.

7.12.2 Participant Replacement

Participants who withdraw from the study will not be replaced.

Participants who are withdrawn due to a positive COVID-19 infection prior to completing <2 days (48hrs) on study may be replaced at the discretion of the investigator.

7.12.3 Lost to Follow-Up

A participant will be considered lost to Follow-Up if they repeatedly fail to attend scheduled visits/contacts/telehealth assessments and are unable to be contacted by the study site.

The following actions will be taken if a participant fails to attend a scheduled visit/contact/telehealth assessment:

- The investigator/site/regional center must attempt to contact the participant and reschedule the missed assessment(s) as soon as possible. They must counsel the participant on the importance of maintaining the assigned assessment schedule and ascertain whether or not the participant wishes to and/or should continue in the study.
- Before a participant is deemed lost to Follow-Up, the Investigator or designee (i.e. regional call center) must make every effort to regain contact with the participant/emergency contact (where possible, 3 telephone calls and, if necessary, a certified letter to the participant's last known mailing address or local equivalent methods). These contact attempts should be documented in the participant's medical record.
- Should the participant continue to be unreachable, they will be considered to have withdrawn from the study.

7.13 Study Stopping Rules

A formal plan for interim data monitoring for futility will be established. Review of serious, unexpected, and related AEs by the CRO Medical Monitor, Data Safety Monitoring Board (DSMB), IRB, or HC/ FDA or applicable relevant local/national regulatory authorities may also result in suspension of further study agent administration. Health Canada/FDA/IRB/or local/national regulatory authority and study Sponsor(s) retain the authority to suspend additional enrollment and study agent for the entire study, as applicable.

7.14 Appropriateness of Measurements

All assessments used in the study are considered standard (ie, widely used and generally recognized as reliable, accurate, and relevant).

8 CLINICAL TRIAL MATERIALS

8.1 Study Treatment Supplies

8.1.1 Nitric Oxide Nasal Spray and Placebo

Supplies of NONS and placebo are described in Table 1.

Table 1 Identity of Investigational Product

Study Drug	Formulation
Nitric oxide spray (supplied by the Sponsor)	12.5 mL formula A in saline in one chamber, and 12.5 mL formula B in saline in the other chamber of the dual chamber nasal spray device which delivers a metered dose
Placebo (supplied by the Sponsor)	Sterile 0.9% Sodium Chloride, USP

8.2 Packaging and Labeling

The drug will be prepared and packaged in an ISO 13485 and GMP registered facility. The NONS solution will be prepared in three 25 mL bottles of manual pump nasal spray bottles with the labeled statement according to local regulatory guidelines for labeling "for investigational use only" with minimally the lot/batch number, expiry date, and storage conditions.

8.3 Distribution and Supply Management

Regional distribution and supply management is a critical piece to the overall success of the study. Distribution and supply management following participants' randomization will be completed in accordance with the Supply Management Plan. The Sponsor in conjunction with support vendors, as applicable, will detail how study supplies are received, shipped and returned to sites for both remote and on-site enrolled participants. The Sponsor or designee (ie, CRO or supply management and support vendor(s)) will be responsible for maintaining this document throughout the course of the study.

For more details, refer to the Supply Management Plan.

8.4 Storage and Accountability

8.4.1 Study Treatment Storage

Study treatment provided to participants will be stored, dispensed, and recorded in accordance with this protocol, Pharmacy Manual, Supply Management Plan and other multicenter operational procedures document for this study including participant instructions. Only participants enrolled in the study may receive study treatment.

All study treatment should be stored at temperatures ranging from 2°C to 40°C (35°F to 104°F) and protected from flames and combustible materials. Study medication should be kept out of the reach of children.

8.4.2 Study Treatment Accountability

The Investigator or his/her designee will maintain accurate records of the receipt of all study treatment. In addition, accurate records will be kept regarding when and how much of each study treatment is dispensed, used and unused by each study participant and documented in the eCRF.

8.5 Investigational Product Retention at Sponsor

At the conclusion of the study, any unused or opened study treatment bottles will be returned to the Sponsor or designee for accountability tracking (refer to the Supply Management Plan). The Sponsor should not dispose of any used or unused study drug until drug accountability is performed by the Sponsor or its designee.

8.6 Preparation of Study Treatment

There is no preparation of the study treatment required.

8.7 Use of the Spray Bottle

In the event of a malfunction of the spray bottle, or the participants misplace the spray bottle, participants should contact the regional study center for further instructions.

At the end of the study, or at the time of participant discontinuation or early termination, nasal spray bottles will be returned to the Sponsor as described in the MOP/IOP.

Participants will complete the spray bottle PRO on Day 1 and Day 5, documenting their perception of the ease of use of the spray bottle (Appendix 3).

9 PLANNED STATISTICAL METHODS

9.1 General Considerations

A detailed statistical analysis plan will be developed separately and finalized prior to randomization of the first participant. Deviations from the protocol-planned analyses will be noted.

The statistical analysis of the data obtained from this study will be performed using SAS® Version 9.4 or higher. All statistical tests will be performed at the 0.05 (two-sided) significance level, unless otherwise noted.

The data collected in this study will be documented using summary tables and participant data listings. Continuous variables will be summarized using descriptive statistics, specifically the number of observations, mean, median, standard deviation, minimum and maximum. Categorical variables will be summarized by frequencies and percentages. The analysis of both efficacy and safety parameters will be conducted for each treatment group separately. Active treatment will be compared against placebo.

Baseline characteristics will be summarized using descriptive statistics or frequencies and percentages, as appropriate. No statistical hypothesis tests will be performed on these characteristics.

9.2 Determination of Sample Size

For an annualized infection rate of 3% in the placebo arm (daily incidence = 0.000075), and assuming a true hazard ratio of 0.15 implying protective effect of NONS equivalent to a vaccine efficacy of 85%, a sample size of 11,480 participants randomized 1:1 (NONS:Placebo) and available in the modified intent-to-treat (mITT) population will provide 90% power to demonstrate superiority of NONS to placebo in preventing COVID-19 infections reported through 28 days, based on Cox regression model and a 2-sided 0.05-level test (Schoenfeld 1983). The expected number of events in the two arms is 2 and 10 for the NONS and placebo groups respectively. This further assumes 25% censoring during the 28-day period (1.05% loss per day).

Sample size calculations conducted under version 1.0 of the protocol (dated April 27, 2021) used estimates of annualized case rates as listed in Table 2. At that time, the recent estimated annualized infection rate based on confirmed cases ranged from 2.2 through 3.9% in select Canadian provinces, though there was considerable variability, and these rates underestimate the true infection rates considering those untested. The US and other nations may have substantially higher infection rates and require fewer subjects to be randomized.

In particular, for the Czech Republic, Slovakia, and Sri Lanka, the reported annualized rates are between 0.14% and 8.23%, 0.07% and 7.27%, and 1.48% and 6.18% respectively over the period of May 1, 2021, to July 31, 2021. We are therefore likely to have sufficient power to conduct this study in those countries.

The maximum number of participants who will be randomized is 13,000, in order to achieve a maximum of 11,480 participants initiating their randomized treatment assignment and entering the mITT population. If the infection rate is higher than assumed here, enrollment and randomization will be closed if the total number of COVID-19 events in the mITT population exceeds 18 cases, 50% more than the number expected for 90% power. This inflation accounts for the increased infection rate and the consequent increased risk of infection between the time of randomization and time of initiation of study treatment due shipping times.

Table 2 Daily COVID-19 Counts

Population	Estimated annualized rate in February 2021	Equivalent date based on study in control arm	assumption	Days Daily Confirmed case counts exceeded 3% / 4% annualized rate		
	(through 25FEB2021		4% annualized rate	1FEB-25FEB2021		
Manitoba	2.2%	104	138	4 / 0 Days		
Alberta	2.8%	328	437	12 / 1 Days		
British Columbia	3.2%	380	507	21 / 3 Days		
Quebec	3.9%	637	849	25 / 15 day		
Ontario	2.9%	1101	1468	11 / 4 days		
Canada (all provinces)	3.0%	2819	3759	20 / 2 days		
United States	> 4%	24,615	32,820	25 days		

Source: https://www.canada.ca/en/public-health/services/diseases/2019-novel-coronavirus-infection.html

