4 STUDY POPULATION SELECTION

4.1 Study Population

The study population will consist of healthy volunteer males and females of any ethnic background aged at least 18 years of age with no prior history of a COVID-19 infection, or current SARS-CoV-2 infection.

If allowed by local regulations, participants will be recruited through public announcements and social media as approved by the ethics review board(s). Ideally, cooperation with Public Health Officials will aid in identifying "hotspots" where focused advertising for recruitment will be targeted. A study website may be set up to support initial interest and screening efforts. Additional efforts to support study visibility and broaden recruitment areas to more remote locations, will be assessed throughout the course of the study such as television or radio advertising. Local/national regulations regarding recruitment of participants for clinical research will be applied in each country.

Participants may be recruited in multiple countries, starting in Sri Lanka, using a multicenter method, it is estimated that up to 13,000 participants will be randomized with an anticipated 11,480 participants initiating study treatment. A screened participant is defined as someone who has expressed interest in the study but has not completed the consent and randomization process.

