9.5 Analysis of Efficacy

9.5.1 Primary Efficacy Analysis

The primary efficacy objective is to demonstrate that NONS product reduces the risk of COVID-19 infection. The associated null hypothesis is that the hazard ratio (HR) of NONS relative to placebo is greater than 1, or H_0 : $HR \ge 1$, or equivalently in terms of a vaccine efficacy, H_0 : $VE \ge 0$ where vaccine efficacy is calculated as VE = 100% x (1-HR). The HR will be estimated using a Cox proportional hazard regression model with a fixed effect only for treatment arm. Due to the small, expected event rate (see the Section 9.2), incorporation of additional fixed effects may not be possible. However, as a sensitivity analysis, a stratified Cox model using randomization strata (≥ 65 , <65 at increased risk, < not at increased risk) will also be fit. Similarly, age-group (\ge /<65) and region-specific models will be fit, aggregating adjacent provinces, states, or larger geographies to enable model convergence and evaluate, to the extent possible, whether differences exist.

The primary analysis will be executed in the mITT data set and count all cases occurring starting from the day after participants begin administering study treatment.

For all models, a 2-sided score-based 95% confidence interval (CI) and 2-sided p-value for the effect of NONS will be calculated.

The estimand of the primary analysis is a treatment policy strategy and will consider intercurrent events as censored. Specifically, participants who stop administering NONS for any reason, stop submitting data to the electronic patient-reported outcomes (ePRO) system, do not submit paper diaries, or are unreachable by telephone contact, will be censored on the day of their last ePRO clinical status submission or last available documented day on paper diary (ie, the last day confirming no positive COVID-19 test). Participants who submit COVID-19 test results following Day 28, will be censored at Day 28. Participants submitting a COVID-19 test result on or prior to Day 28 will be considered to have reached the primary endpoint on the day that the specimen (ie, nasal swab) is collected, not the date of the test. Positive test results obtained within 48 hours of randomization will be considered infected at randomization and not counted as events.

The Cox model will be fit to the following sets (if different) as sensitivity analyses:

- mITT set counting all cases after randomization,
- PP set counting cases after first administration,

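### The stated 90% power comes from a large-sample formula that is too optimistic at about 12 events and HR 0.15; score-test power is about 77%, or 81% at a true 3% per year, and 3% per year does not match 0.000075 per day

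*Combined protocol and SAP*

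**What the plan says.** Section 9.2 (Determination of Sample Size), repeated in the synopsis, claims that 11,480 participants in the mITT population, randomized 1:1, "will provide 90% power to demonstrate superiority of NONS to placebo in preventing COVID-19 infections reported through 28 days". The basis is the Schoenfeld formula for a Cox model (cited in 9.2) with a two-sided 0.05 test, a hazard ratio of 0.15 and 25% censoring over 28 days. The rate assumption reads "For an annualized infection rate of 3% in the placebo arm (daily incidence = 0.000075"). The event assumption reads "The expected number of events in the two arms is 2 and 10 for the NONS and placebo groups respectively".

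Two later statements in Section 9.2 lean on the 90%. Enrollment closes if the case count "exceeds 18 cases, 50% more than the number expected for 90% power". After quoting annualized rates for the Czech Republic, Slovakia and Sri Lanka, the section concludes: "We are therefore likely to have sufficient power to conduct this study in those countries".

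Section 9.5.1 plans a Cox model with treatment as the only term, for which "a 2-sided score-based 95% confidence interval (CI) and 2-sided p-value for the effect of NONS will be calculated". It recognises the sparse data when it limits the covariates ("Due to the small, expected event rate (see the Section 9.2"), but no small-sample check of the power is given.

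**The concern.** The Schoenfeld formula treats the log hazard ratio estimate as normal, with variance 4/D for D events in a 1:1 trial. That works for many events and a hazard ratio near 1. Here about 12 events are split roughly 10 to 2, so the test statistic takes only a few values and its distribution under HR 0.15 is far from the assumed one. A stated 90% may then be well off.

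Readers of the plan take the 90% as a 1-in-10 risk of missing a true 85% effect. The same figure also supports the description of the 18-case threshold as holding a 50% margin, and the statement that power is likely to be sufficient in the three countries. Section 4.1 says: "Participants may be recruited in multiple countries, starting in Sri Lanka, using a multicenter method". Sri Lanka's quoted rate reaches down to 1.48% per year.

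The two forms of the planning rate also disagree with each other.

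**Working it through.** **Inputs (Section 9.2).** 5,740 per arm; placebo hazard 0.000075 per day; HR 0.15; 28 days; 25% loss; two-sided 0.05.

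**1. The plan's own figure.** Events needed: D = 4(1.960 + 1.2816)² / (ln 0.15)² = 11.68. For expected events, take exponential loss with rate −ln(0.75)/28 = 0.01027 per day, which gives a mean follow-up of (1 − 0.75)/0.01027 = 24.3 days. Placebo: about 5,740 × 24.3 × 0.000075, or 10.46 after allowing for the events themselves. NONS: 1.57. Total: 12.04. Schoenfeld power at 12.04 events: Φ(√12.04 × |ln 0.15| / 2 − 1.960) = 90.8%. The 90% is reproduced, and the stated 10 and 2 are the rounded counts.

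**2. The rate.** 0.000075 × 365 = 0.0274, or 2.74% per year. A rate of 3% per year is 0.03/365 = 0.0000822 per day. At that rate the expected events are 11.47 + 1.72 = 13.19.

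**3. Power from the distribution of the counts.** With rare events the arm counts are close to independent Poisson variables: y on placebo, x on NONS. For each test, add the probabilities of all pairs (x, y) that reject in favour of NONS. The score test rejects when (y − x)/√(x + y) > 1.96. The exact test is binomial with probability 1/2, given x + y.

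| Test | 0.000075/day (12.04 events) | 3%/365 (13.19 events) |
|---|---|---|
| Schoenfeld formula | 90.8% | 93.1% |
| Score | 76.9% | 81.0% |
| Likelihood ratio | 83.0% | 85.8% |
| Exact conditional | 68.1% | 73.4% |
| Wald (no rejection if NONS has 0 events) | 50% | 58% |

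A simulation of individual participants with the full log-rank (Cox score) test, 100,000 replicates per rate, gave 76.9% and 81.1%.

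**4. A check by hand.** Suppose exactly 12 events occur. The score test needs (12 − 2x)/√12 > 1.96, so x ≤ 2; the exact test has the same limit. Under HR 0.15 each event falls on NONS with probability 0.15/1.15 = 0.1304. Then P(X ≤ 2 | 12, 0.1304) = 80.1%.

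**5. What 90% would take at N = 11,480.**

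| Test | Expected events | Placebo rate per year |
|---|---|---|
| Score | 16.7 | 3.8% |
| Likelihood ratio | 15.4 | 3.5% |
| Exact conditional | 18.9 | 4.3% |

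For the score test 18/16.69 = 1.08, so 18 cases is about 8% above the expected number that gives 90%. At an expected 18 events, score-test power is 92%.

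**6. Score-test power at the ends of the quoted country ranges.**

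| Country | Rate per year | Expected events | Power |
|---|---|---|---|
| Sri Lanka | 1.48% to 6.18% | 6.5 to 27.1 | 49% to 99% |
| Czech Republic | 0.14% to 8.23% | 0.6 to 36.1 | <1% to >99% |
| Slovakia | 0.07% to 7.27% | 0.3 to 31.9 | <1% to >99% |

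The 3.8% needed lies inside all three ranges.

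**7. For scale only.** Reaching 90% by size with the score test would take about 15,900 mITT participants at 0.000075 per day, or about 14,500 at a true 3% per year. Both exceed the maximum of 13,000 randomized.

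**The case against.** The strongest reply is that the plan names its method, applies it correctly and shows the event counts behind it. The power point is therefore a criticism of method; the only arithmetic error is the rate, and that is conservative. This is right, and the point is made on that footing. The sentence in the plan, though, is about the power of the trial, and no standard test delivers 90% at the stated inputs.

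The protocol attaches the word score-based to the confidence interval and does not say which test gives the p-value. This stands in part. The score test is the natural reading, but with the likelihood ratio test the shortfall at a true 3% per year is only about 4 points. The test should be named first and the power then stated for it.

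The 18 is a realised count, while 16.7 is an expected one. At fixed totals, score-test power moves in steps: 80.1% at 12, 76.5% at 13, 90.1% at 14, 87.8% at 15, 95.2% at 16 and 92.5% at 18. On that scale 18 is 29% above the first total that reaches 90% (18/14) and 12.5% above 16 (18/16). The 8% uses the plan's own basis, an expected number. On neither basis is the margin 50%.

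The country minima come from a three-month window and need not persist, and Section 9.6 re-projects the case count during the trial. The lowest-rate figures are therefore extremes, not forecasts. Neither that projection nor the 18-case rule supplies events at the planning rate, so neither restores the 90%.

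**Conclusion.** The concern holds. At 0.000075 per day and HR 0.15, score-test power is about 77%; at a true 3% per year it is about 81%. The other tests run from about 50% (Wald) to 86% (likelihood ratio at 3%), all below 90%. With the score test, the risk of missing a true 85% effect is 19% to 23%, about twice what the plan implies.

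The rate mismatch is a separate error. The daily figure is about 9% below 3%/365 (0.000075/0.0000822 = 0.91), which slightly lowers the expected events and does not cause the shortfall.

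The result rests on the plan's own sample size, hazard ratio and censoring, with a constant hazard and exponential loss. The 18-case closing rule is not harmed; only its description is. Type I error and the futility rule are not in question here.

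**What to change.** Change the text of Section 9.2, and of the synopsis where it repeats the same statements:

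- Name the test that gives the primary p-value and state the power for it. With the score test this is about 77% at 0.000075 per day (12 expected events), or about 81% at a true 3% per year (13.2 expected events). If another test is named, use its figures from the table in step 3.
- Use one rate: 2.74% per year with 0.000075 per day, or 3% per year with 0.0000822 per day.
- State that 90% power with the score test needs about 17 expected events, or about 3.8% per year at this sample size. Describe 18 as 50% above the 12 events expected at the planning rate (18/12 = 1.5). Leave the closing rule and its shipping-time reason unchanged.
- Qualify the three-country sentence: about 3.8% per year is needed for 90%, a rate inside the quoted ranges but not met at their lower ends.

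The cost is a few sentences and a less favourable stated power. Sample size, analysis, closing rule and conduct do not change.

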Interim Analysis: Given the small number of expected events, there will be no interim analysis for efficacy. Participant enrollment may be closed before 11,480 subjects have entered the mITT population if 18 cases are accumulated, but this will be considered the final analysis, not an interim analysis.

Date of Original Approved Protocol: 12 May 2021

Document History Summary

Version / Date	Summary of Revisions
1.0 / 12 May 2021	Original Protocol
1.1 / 11 Aug 2021	Modification to a Multicenter trial from a decentralized trial. Expanded language to be globally relevant. Study product administration details added for clarity. Daily use population analysis added. EudraCT Number added. Administrative updates.
1.2 / 08 Dec 2021	Eligibility, updated to include an allowance of prior COVID-19 vaccination. Expanded option for paper-based questionnaire collection. Removal of antibody testing requirements. Relationship between Adverse Event and Study Drug, updated. Administrative updates.

LIST OF ABBREVIATIONS AND DEFINITIONS OF TERMS

Abbreviation Definition

ACE Angiotensin converting enzyme

AE Adverse event

CCID₅₀ Cell culture infectious dose 50%

CFR Code of federal regulations

CI Confidence interval

DMC/DSMC Data monitoring committee/Data Safety and Monitoring Committee

eCRF Electronic case report form

ePRO Electronic patient-reported outcomes

CRO Clinical Research Organization

ER/ED Emergency room/emergency department

GCP Good Clinical Practice

HC Health Canada

HR Hazard ratio

ICH International Council for Harmonisation

ICF Informed consent form

ICMJE International Committee of Medical Journal Editors

IEC Independent ethics committee

IOP Internal Operating Procedures

IND Investigational new drug

IRB Institutional review board

IWRS Interactive web response system

MedDRA Medical dictionary for regulatory activities

MOP Manual of procedures

mITT modified intent-to-treat

NO Nitric Oxide

NONS Nitric oxide nasal spray

NORS Nitric oxide releasing solution

PCR Polymerase chain reaction

PP per protocol

RT-PCR Real-time polymerase chain reaction

SAE Serious adverse event

SD Standard deviation

SDV Source data verification

Suspected unexpected serious adverse reaction **SUSAR**

VE Vaccine efficacy

WHO World Health Organization SaNOtize

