9.6 Interim Analysis

Given the small number of expected events, there will be no interim analysis for efficacy. As described in Section 9.2, the enrollment may be closed when 18 cases are accumulated, but this will be considered the final analysis, not an interim analysis.

After every approximately 2,000 participants from the mITT cohort complete the study, the aggregated COVID case-rate will be used to calculate the projected number of cases for the full sample size of 11,480. The study may be considered futile if fewer than 10 cases are projected to be observed for the full sample size.

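### The event-driven closing rule is mandatory after 18 cases in Section 9.2 but discretionary at 18 in Section 9.6 and the synopsis, and neither the data cut nor the qualifying events are defined

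*Combined protocol and SAP*

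**What the plan says.** Three current passages of the combined protocol and SAP give the closing rule.

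- Section 9.2 (sample size), for the case of an infection rate above the assumed one: "enrollment and randomization will be closed if the total number of COVID-19 events in the mITT population exceeds 18 cases". The basis of the number is given as "exceeds 18 cases, 50% more than the number expected for 90% power".
- Section 9.6 (interim analysis), which refers back to 9.2: "the enrollment may be closed when 18 cases are accumulated, but this will be considered the final analysis, not an interim analysis".
- Synopsis, interim analysis paragraph: "Participant enrollment may be closed before 11,480 subjects have entered the mITT population if 18 cases are accumulated". It too calls the result the final analysis.

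Section 9.2 also gives the planning figures: "The expected number of events in the two arms is 2 and 10 for the NONS and placebo groups respectively", with a sample size that "will provide 90% power to demonstrate superiority of NONS to placebo" at a hazard ratio of 0.15 and a two-sided 0.05-level test.

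Section 9.5.1 specifies a Cox model with a two-sided score-based interval and p-value. It counts cases in the mITT set from the day after dosing begins, up to Day 28. It dates each event by specimen collection.

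**The concern.** The passages differ in count (the 19th case against the 18th) and in force (will against may). Two of the three make the trigger the final analysis, so the rule helps decide how many events enter the only confirmatory test. With about 20 events, the score test can take only a few values, and its true error rate moves above and below 5% as the event count changes by one. Two further gaps leave the analysed count open:

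- **Data cut.** The rule closes enrolment. Nothing says what happens to participants who are still dosing when it triggers.
- **Qualifying events.** Section 9.2 justifies the inflation to 18 partly by infections between randomization and the start of treatment. Section 9.5.1 leaves such cases out of the primary analysis. The count that triggers closure need not be the count that is tested.

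**Working it through.** **Inputs (Section 9.2 unless noted).** Hazard ratio 0.15; two-sided 0.05; 90% power; 11,480 participants 1:1, so 5,740 per arm; placebo rate 0.000075 per day; loss 1.05% per day; 28 days. Score test from Section 9.5.1.

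**The plan's own figures reproduce.** Schoenfeld events = 4(1.960 + 1.282)²/(ln 0.15)² = 4 × 10.507/3.599 = 11.68, rounded up to 12. With exponential events and loss, placebo events = 5,740 × [0.000075/(0.000075 + 0.0105)] × [1 − exp(−28 × 0.010575)] = 10.43. The same formula at 0.15 times the rate gives 1.57 on NONS. The total is 12.0, and 1.5 × 12 = 18.

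**Error of the score test given D analysed events.** With 1:1 risk sets and no effect, NONS events x follow Binomial(D, 0.5). The score statistic is z = (D − 2x)/√D, compared with 1.96.

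- D = 18: x = 4 gives z = 10/4.243 = 2.36 (reject); x = 5 gives 1.89 (do not reject). Error = 2 × P(x ≤ 4) = 2 × 4,048/262,144 = 3.1%.
- D = 19: x = 5 gives z = 9/4.359 = 2.06 (reject); x = 6 gives 1.61 (do not reject). Error = 2 × P(x ≤ 5) = 2 × 16,664/524,288 = 6.4%, of which 3.2% is in the favourable direction.

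A simulation of the Cox score test with real risk sets, daily ties and censoring gave 2.9% and 6.3%.

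| Events analysed | 16 | 17 | 18 | 19 | 20 | 21 | 22 | 23 | 24 |
|---|---|---|---|---|---|---|---|---|---|
| Score-test error (%) | 7.7 | 4.9 | 3.1 | 6.4 | 4.1 | 7.8 | 5.2 | 3.5 | 6.4 |

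**Would the cap be reached?** Under no effect, both arms have the placebo rate: 2 × 10.43 = 20.9 expected events at full size. Treating the total as Poisson, the chance of reaching 18 is 76%, and of reaching 19 it is 69%. If the analysis is cut exactly at the trigger, the error averaged over this distribution is 3.6% with closure at 18 and 5.8% with closure at 19.

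**If follow-up continues after closure.** The documents give no overrun figure, so a Poisson number of extra events is assumed here.

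| Mean overrun (assumed) | 0 | 1 | 2 | 3 | 5 |
|---|---|---|---|---|---|
| Trigger at 18: error (%) | 3.1 | 4.8 | 5.4 | 5.5 | 5.4 |
| Trigger at 19: error (%) | 6.4 | 5.7 | 5.7 | 5.5 | 5.4 |

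**Exact conditional test.** Reject when twice the binomial tail is at most 0.05. At 18 events this means x ≤ 4, with error 3.1%. At 19 it also means x ≤ 4: error = 2 × 5,036/524,288 = 1.9%. At hazard ratio 0.15, the NONS share of events is 0.15/1.15 = 0.130, and power is 92.5% at 18 events and 90.9% at 19. The score test at 19 has 97.1%, but with an error of 6.4%.

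**The case against.** The strongest reply is that the rule closes enrolment, not follow-up. The endpoint runs to Day 28, and nothing says that participants already dosing are dropped. Calling closure the final analysis may mean only that no alpha is spent on an interim look. If everyone enrolled is followed to Day 28, events accrue past the trigger and the two readings converge. One simulation of the null assumed uniform accrual, which the documents do not specify. It gave 5.3% against 5.2% (trigger 18 against 19) for 60 days of accrual, and 4.7% against 5.4% for 365 days. This stands, and it limits the error claim. A reader might infer that the choice between 18 and 19 decides whether the test holds 5%. The documents do not support that, because they do not fix the analysed count at the trigger.

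The excess over 5% also comes from applying an asymptotic test to few events, not from the wording. Cutting at the 18th event would not by itself secure 5%: 24% of null trials would never reach 18, and the error among those is 5.1%. This stands too, and is why the fix includes an exact test.

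A reader might also infer that the optional wording lets the sponsor choose a favourable moment. The documents do not support this. The count is pooled across arms, and Section 5.5 restricts treatment codes to distribution-center staff and unblinded CRO staff.

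Finally, Section 9.5.1 leaves termination criteria to a separate SAP. A later document could add detail, but the three passages would still disagree.

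**Conclusion.** The contradiction is real and wrong as written: one decision threshold has two counts and two degrees of obligation, in current text. The missing data cut and the mismatch between triggering and analysed events compound it.

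The effect on type I error is conditional. If the analysis contains exactly the triggering count, the two readings give 3.1% and 6.4% (3.6% and 5.8% averaged over the plan's own null event distribution). With an assumed mean overrun of 2 events the gap is 5.4% against 5.7%, and with 3 it is effectively nil at about 5.5%. So under one set of readings the stated 0.05 level depends on which section is followed. Under another, both readings exceed it slightly.

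These figures assume 1:1 risk sets, the plan's event and loss rates, and Poisson totals and overrun.

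**What to change.** 1. In the synopsis, Section 9.2 and Section 9.6, state one rule with one count and make it mandatory.
2. Count toward it only events eligible for the primary analysis, that is, those meeting the Section 9.5.1 definition.
3. State whether the primary analysis is cut at the trigger or run after all enrolled participants reach Day 28. If it is cut at the trigger, say how a positive reported later with an earlier specimen date is handled.
4. Base the primary p-value on an exact conditional test of the split of events between arms, which holds 5% at any count. The Cox hazard ratio can stay as the estimate, with an interval that agrees with the exact test.

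The cost is wording in three places plus a change of test in Section 9.5.1. The exact test is somewhat conservative: at hazard ratio 0.15 its power is about 92.5% at 18 events (the same rejection region as the score test) and 90.9% at 19, both above the planned 90%.
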